6.4 SUBGROUPS

No subgroup analysis is planned.

6.5 POOLING OF CENTRES

This section is not applicable, because the study was performed in one centre only.

6.6 HANDLING OF MISSING DATA AND OUTLIERS

6.6.1 Safety data

With respect to safety, it is not planned to impute any missing values except for missing dates.

Missing or incomplete adverse event (AE) dates will be imputed according to Boehringer Ingelheim (BI) standards “Handling of missing and incomplete AE dates” (001-MCG-156_RD-01[1]).

6.6.2 Pharmacokinetic data

Missing data and outliers of PK data are handled according to “Noncompartmental Pharmacokinetic Analyses of Clinical Studies” (001-MCS-36-472_RD-01 [2]).

6.6.3 Pharmacodynamic data

Missing data and outliers of PD data are handled as PK according to “Noncompartmental Pharmacokinetic Analyses of Clinical Studies” (001-MCS-36-472_RD-01 [2]).

6.7 BASELINE, TIME WINDOWS AND CALCULATED VISITS

For safety evaluation (except for ECG), the baseline will be defined as the last available measurement prior to the first dabigatran administration.

For PD parameters of individual subject, the baseline (E_{base}) is defined as the arithmetic mean values at Day -1 and Day 1 [0:00]. The E_{base} will be used for individual calculation of the ratio of PD parameters [PD value at each timepoint/ E_{base}].

For all parameters [REDACTED], dTT and [REDACTED], reversal to baseline is defined as a coagulation test value being below the upper limit normal (ULN) as determined based on the pre-dose values of the coagulation parameter prior to dabigatran drug administration in this study. In addition, reversal to baseline will be calculated using the ULN as determined based on the pre-dose values in studies of 1321.1 and 1321.2 ([Table 6.7: 1](#)) as sensitivity analysis.

Table 6.7: 1

Upper limit normal values for PD parameters

[REDACTED]	[REDACTED]	dTT [s]	[REDACTED]	[REDACTED]
ULN	[REDACTED]	35.5	[REDACTED]	[REDACTED]

7. PLANNED ANALYSIS

For End-Of-Text tables for non-PK parameters, the set of summary statistics is: N / Mean / SD / Min / Median / Max.

Tabulations of frequencies for categorical data will include all possible categories and will display the number of observations in a category as well as the percentage (%) relative to the respective treatment group (unless otherwise specified, all subjects in the respective subject set whether they have non-missing values or not). Percentages will be rounded to one decimal place. The category missing will be displayed only if there are actually missing values.

7.1 DEMOGRAPHIC AND OTHER BASELINE CHARACTERISTICS

Only descriptive statistics are planned for this section of the clinical trial report (CTR). Demographic variables are described in [Section 5.4.1](#).

7.2 CONCOMITANT DISEASES AND MEDICATION

Frequency tables are planned for this section of the CTR. Concomitant diseases will be coded using the coding system of the Medical Dictionary for Drug Regulatory Activities (MedDRA). Medications will be coded using the World Health Organization Drug Dictionary Enhanced/Herbal (WHO-DDE).

7.3 TREATMENT COMPLIANCE

Idarucizumab will be administered and monitored by the investigator, [] deputy or members of [] staff. The measured plasma concentrations of Idarucizumab will provide information regarding compliance. It is not intended to list the compliance separately.

7.4 PRIMARY ENDPOINT

The analysis of PK parameters is performed according to “Noncompartmental Pharmacokinetic Analyses of Clinical Studies” (001-MCS-36-472_RD-01 [[2](#)]).

Comparative figure of PD parameter of dTT (dTT: AUEC_{above, 2-12} on day 4 without Idarucizumab and day 11 with Idarucizumab) will be presented in the presence or absence of Idarucizumab.

The following analyses will be performed:

- Percent (%) of subjects with dTT values (at least one value) reversed to baseline within time frame [completion of first infusion of Idarucizumab, completion of second infusion of Idarucizumab].
- Percent (%) of subjects with dTT values (all values) reversed to baseline for 2, 4, 6, 12 or 72 hours after completion of first infusion of Idarucizumab.

[figure not shown]
AUEC₂₋₁₂ of individual subject will be calculated from dTT ratio. AUEC_{above, 2-12} based on dTT ratio will be calculated by subtracting the area under the 1 between 2 and 12 hour (1x

10[hrs]) after administration of Dabigatran from AUEC₂₋₁₂ based on dTT ratio (see also, “Noncompartmental Pharmacokinetic Analyses of Clinical Studies” (001-MCS-36-472_RD-01 [2])).

The percent (%) reduction in dTT of AUEC_{above, 2-12} based on dTT ratio from day 11 compared to day 4 will be explored.

7.5 SECONDARY ENDPOINTS

The analysis of PK parameters for secondary endpoints is performed according to “Noncompartmental Pharmacokinetic Analyses of Clinical Studies” (001-MCS-36-472_RD-01 [2]).

7.7 EXTENT OF EXPOSURE

Frequency and percentage of patients will be summarized by Idarucizumab doses used.

7.8 SAFETY ANALYSIS

All safety analyses will be performed on the treated set.

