If a subject is withdrawn from the trial prior to administration of any trial medication, the data of this subject will not be entered in the trial database and not be reported. If a subject discontinues or withdraws from the trial thereafter, this will be documented and the reason for withdrawal will be recorded in the clinical report forms (CRFs), the data will be included in the trial database and will be reported. At the time of discontinuation a complete end-of-treatment evaluation will be performed if possible and the information will be recorded in the CRFs. Those withdrawals will be discussed in the final report of the trial.

In case that not all subjects complete the dose level, the TCM together with the TCPK and the TSTAT decide if and how many subjects will be replaced. Each subject will have a unique subject identification number including replacing subjects.

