3.3.4.2 Discontinuation of the trial by the sponsor

Boehringer Ingelheim reserves the right to discontinue the trial overall or at a particular trial site at any time for the following reasons:

1. Failure to meet expected enrolment goals overall or at a particular trial site
2. Emergence of any efficacy/safety information invalidating the earlier positive benefit-risk-assessment that could significantly affect the continuation of the trial
3. Violation of GCP, the CTP, or the contract disturbing the appropriate conduct of the trial

The Investigator / the trial site will be reimbursed for reasonable expenses incurred in case of trial termination (except in case of the third reason).

Early discontinuation of the trial by the investigator

1. dosing will be stopped immediately in case if clinically relevant allergic reaction/ hypersensitivity (e.g. fever > 39°C, dyspnoea, rush) occurs which needs medical intervention
2. due to occurrence of signs of any intercurrent illness during the dosing
3. due to an adverse event, sufficiently severe to contraindicate continuing the trial
4. occurrence of a major bleeding, or sustained minor bleedings which cannot be controlled with the local haemostasis, any other bleeding event considered clinically relevant by the investigator, or positive haemocult test during the trial

The investigator can be guided by the criteria above, but may discontinue subjects at any time based on his/her clinical judgment.

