4.1.1 Identity of the Investigational Medicinal Products

The investigational product idarucizumab and NIMP dabigatran will be supplied by Boehringer Ingelheim Pharma GmbH & Co. KG, Germany. The compositions of these drugs are detailed in Table 4.1.1: 1 and Table 4.1.1:2.

Table 4.1.1: 1 Investigational product

Substance:	Idarucizumab(BI 655075)
Pharmaceutical formulation:	50 mL solution for iv infusion
Source:	Boehringer Ingelheim Pharma GmbH & Co. KG, Germany
Unit strength:	50 mg/mL
Posology	2 short infusions of 2500 mg each 15 minutes apart
Route of administration:	intravenous (iv) infusion

Table 4.1.1: 2 Non-Investigational product

Substance:	Dabigatran etexilate
Pharmaceutical formulation:	capsules
Source:	Boehringer Ingelheim Pharma GmbH & Co. KG, Germany
Unit strength:	110 mg
Posology	3 days 220 mg twice daily (b.i.d) with a single dose 220mg on day 4
Route of administration:	oral (po)

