6.2.2 Treatment periods

Subjects will be institutionalized on day -1. The following investigations will be performed:

- Physical examination including AE questioning
- Clinical laboratory,

Each subject will receive multiple doses of dabigatran etexilate 220 mg b.i.d. from day 1 to 3 with a single dose on day 4 and from day 8 to 10 with a single dose on day 11, 2 doses of idarucizumab will be administered intravenously approximately 1hour 55 minutes and 2 hours 15 minutes after the last dose of dabigatran etexilate on day 11.

Subjects will be kept under close medical surveillance and will stay in the trial site for at least 72 hours after the idarucizumab dose. Subjects will be allowed to leave the trial site after formal assessment and confirmation of their fitness by the investigator or designee.

The measurements performed during the treatment period are specified under [Section 5.3](#) and in the [Flow Chart](#). For details on time points for all trial procedures, see Flow Chart.

In general, if several measurements including venipuncture are scheduled for the same point of time, venipuncture should be the last of the measurements due to its inconvenience to the subject and possible influence on physiologic parameters.

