7.3 PLANNED ANALYSES

All statistical analyses will be based on the treated set.

Treated set:

This subject set includes all subjects who received the investigational drug.

When necessary, PK/PD set may be created for PK/PD analysis, details will be described in the TSAP.

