6.3 PATIENT SETS ANALYSED

All analyses will be based on the treated set.

- Treated set (TS):
This subject set includes all subjects who received the idarucizumab.
- Pharmacokinetic set (PKS):
This subject set includes all subjects who received the idarucizumab and who had at least one PK parameter.
- Pharmacodynamic set (PDS):
This subject set includes all subjects in the TS who provide at least one evaluable predose and/or one on-treatment PD observation after the start of administration of dabigatran. This analysis set is used for all PD analyses.

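### Safety tables are limited to subjects who received idarucizumab, so a subject stopped by an adverse event on dabigatran alone is counted in no 'dabigatran period' frequency

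*SAP*

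**What the plan says.** SAP 7.8 fixes the population for every safety output: "All safety analyses will be performed on the treated set". SAP 6.3 defines the treated set: "This subject set includes all subjects who received the idarucizumab". Protocol 7.3 words it slightly differently: "This subject set includes all subjects who received the investigational drug". The two agree, because Protocol 4.1.1 separates the two drugs: "The investigational product idarucizumab and NIMP dabigatran will be supplied by". Dabigatran is the non-investigational product, so taking it does not put a subject in the treated set. Neither document defines a wider safety set.

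On timing, Protocol 6.2.2 says: "2 doses of idarucizumab will be administered intravenously approximately 1hour 55 minutes and 2 hours 15 minutes after the last dose of dabigatran etexilate". That last dose is on day 11.

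Protocol 7.3.4 and SAP 6.1 assign safety data from first dabigatran intake to first idarucizumab intake to a separate interval, the 'dabigatran period'. Protocol 3.1 gives assessment of the safety of 220 mg b.i.d. as the purpose of the dabigatran-alone period. Protocol 2.3 repeats this and allows that bleeding risk may be raised at this dose.

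On stopping, Protocol 3.3.4.2 lists major bleeding, uncontrolled minor bleeding, and "any other bleeding event considered clinically relevant by the investigator, or positive haemocult test during the trial". Protocol 4.2.1 says to stop trial medication for a major bleed. On replacement, Protocol 3.3.4.1 says that "the TCM together with the TCPK and the TSTAT decide if and how many subjects will be replaced". For a subject who withdraws after taking trial medication, the same section says that "the data will be included in the trial database and will be reported".

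**The concern.** Membership of the treated set is decided on day 11, after the whole dabigatran exposure that the 'dabigatran period' tables describe. A subject can fail to reach day 11 because of the very event those tables count. The table would then describe 220 mg b.i.d. only in subjects who tolerated it well enough to finish: bleeds that end dosing drop out, and milder ones stay.

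Replacement can make the loss hard to see, because the table may still show N = 12. Protocol 2.2 also plans to compare safety between Chinese, Japanese and Caucasian volunteers, so a frequency that is too low here could carry into that comparison.

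**Working it through.** The plan gives no figure to reproduce. Protocol 7.7 sets N = 12 by custom, and no stopping rate is stated. The check is of the set logic first, then of the size of the effect.

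**1. Order of dosing.** Flow Chart 2 gives two courses of 3 days b.i.d. plus one dose: 2 × (3 × 2 + 1) = 14 dabigatran doses, the last at 240:00. Idarucizumab starts at 241:55. Every dabigatran dose precedes entry to the treated set.

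**2. Who is counted.** SAP 7 takes percentages relative to the subjects in the respective set. A subject stopped before 241:55 is outside the treated set, and so outside both numerator and denominator.

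**3. Direction of the effect.** Let d be the number who start dabigatran, s the number who stop before idarucizumab because of a given event, and a the number who have that event and continue.

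- As planned: a/(d − s).
- All dosed subjects: (a + s)/d.
- Difference (all dosed minus planned): s(d − a − s)/[d(d − s)]. This is positive when s > 0, unless every subject has the event.

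For u stops without the event, the planned figure is a/(d − u) against a/d. Only the denominator shrinks, so the planned percentage is the same (a = 0) or slightly higher. With a = 1, d = 12 and u = 1 it is 1/11 = 9.1% against 1/12 = 8.3%.

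**4. Size for one event-driven stop** (the count is assumed; a = 0; Clopper-Pearson 95% intervals):

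| Case | As planned | All dosed |
|---|---|---|
| Not replaced | 0/11 = 0% (0 to 28.5%) | 1/12 = 8.3% (0.2 to 38.5%) |
| Replaced | 0/12 = 0% (0 to 26.5%) | 1/13 = 7.7% (0.2 to 36.0%) |

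The formula gives the same differences: 1 × 11/(12 × 11) = 8.3 points and 1 × 12/(13 × 12) = 7.7 points. The intervals only show the precision; the plan does not call for them.

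**5. How likely is it?** The nearest rate in the documents is major bleeding in RE-LY, about 3% per year (Protocol 1.1). Protocol 2.1 and 2.3 say that 220 mg b.i.d. was chosen to give healthy subjects concentrations similar to those in RE-LY. Applied to the 10 days from 0:00 to 240:00:

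- per subject: 3% × 10/365 = 0.082%;
- at least one of 12: 1 − (1 − 0.00082)^12 = about 1%.

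This is a rough anchor. It comes from patients rather than healthy volunteers, and it covers major bleeding only, whereas the stopping criteria reach further. The actual chance of an event-driven stop could be higher, but the documents do not say by how much. For scale only, an assumed per-subject risk of 2% would give 1 − 0.98^12 = 21.5%.

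**The case against.** The strongest reply is that the case cannot be lost. Protocol 3.3.4.1 puts the subject's data in the database, requires them to be reported, and requires the withdrawal to be discussed in the final report. Protocol 5.3.6.2 collects adverse events from consent onward. In a descriptive trial of 12 subjects with no hypothesis test, one such subject would be read individually. The primary objective is idarucizumab PK and PD, and dabigatran is already marketed in China.

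All of this stands, and it limits the consequence. It does not correct the tables: the reporting requirement names no table, set or denominator, and a narrative does not change a percentage computed without that subject.

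Other parts of the objection also stand:

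- The stopping criteria are guidance. Protocol 3.3.4.2 leaves the decision to the investigator, and Protocol 4.2.1 favours watchful waiting for minor bleeding, so most minor bleeds would stay in the tables.
- The haemoccult criterion adds little. Protocol 5.3.3 schedules occult blood testing only at screening, so after dabigatran starts it could act only through an unscheduled test.
- Protocol 2.3 expects severe events to be very unlikely.

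A reader might infer that a stopping bleed would be concealed, that the bleeding frequency will be too low whatever happens, or that a loss from the tables is likely. The documents support none of these. Reporting is required, the downward bias needs an event-driven stop, and no stopping rate is given.

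**Conclusion.** The gap is real but conditional. As written, the 'dabigatran period' tables can never count a subject whose adverse event ended dosing before idarucizumab, although assessing dabigatran safety is a stated purpose of that period. For one such stop the reported frequency of the event falls by about 8 percentage points (8.3% to 0% without replacement, 7.7% to 0% with it).

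This rests on reading SAP 7.8 literally. The sponsor's adverse event guideline cited in SAP 7.8.1 is not available here, but the SAP itself names the set for all safety analyses. The number of stops is assumed; the chance of even one may be small, about 1% if only major bleeding at the RE-LY rate is considered. If nobody stops early, the sets coincide and nothing changes. No PK or PD endpoint is touched. The change is worth making because it is cheap and because the error, if it occurs, falls on the event of most interest in that period.

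**What to change.** - In SAP 6.3, add a safety set: all subjects with at least one dose of dabigatran etexilate or idarucizumab.
- In SAP 7.8, use it for the 'dabigatran period' column of every safety table, including the serious, AESI and other-significant adverse event tables. Keep the treated set for 'dabigatran + treatment' onward and for PK and PD.
- In SAP 6.1, add an end rule. The interval now closes at first idarucizumab intake, which these subjects never have. For them, close it at their end-of-treatment evaluation (Protocol 3.3.4.1), or at last dabigatran dose plus the 24-hour residual effect period (Protocol 5.3.6.2) if that evaluation is not done.
- Show both Ns, and list each subject who stopped before idarucizumab with the reason.

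The cost is SAP wording, a second denominator and one derivation rule. No new data are needed: these subjects are already in the database, and SAP 7.8.1 already codes adverse events for enrolled subjects. The small downside is that the two treatment intervals may show different Ns.

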7.8.1 Adverse events

The analyses of AEs will be descriptive in nature. All analyses of AEs will be based on BI standards as described in the BI guideline “Handling and summarisation of adverse event data for clinical trial reports and integrated summaries (001-MCG-156 [3]).

All reported AEs for enrolled subjects will be coded with the most recent version of the MedDRA.

For analysis of AE, occurrence data on CRF will be collapsed into one AE as described in the AE guideline. Please refer (1) (3).

The analysis of AEs will be based on the concept of treatment emergent AEs. The assignment of treatment regimen will be based on those defined in the CTP, Section 7.3.4.

Protocol specified adverse events of special interest (AESI) will be used as defined in the CTP, Section 5.3.6.1

According to ICH E3 (4), AEs classified as ‘other significant’ will include those non-serious and non-significant AEs with

- (i) ‘action taken = discontinuation’ or ‘action taken = reduced’, or
- (ii) marked haematological and other lab abnormalities or lead to significant concomitant therapy as identified by the Clinical Monitor/Investigator at a Report Planning Meeting.

An overall summary of AEs will be presented.

The frequency of subjects with AEs will be summarised by treatment, primary system organ class and preferred term. Separate tables will be provided for subjects with drug related AEs, for subjects with serious AEs, for subjects with drug related serious AEs, for subjects with AESI and for subjects with other significant AEs according to ICH E3 (4).

The system organ classes will be sorted according to the standard sort order specified by European Medicines Agency, preferred terms will be sorted by frequency (within system organ class).

Subjects with serious AEs, AESI or other significant AEs will be listed in Section 15.4.2 of the CTR.

7.8.2 Laboratory data

The analyses of laboratory data will be descriptive in nature and will be based on BI standards (5). Descriptive statistics will be calculated for original and normalized (if applicable) values over the time and for the difference from baseline including post examination values. Changes from baseline to last value on treatment in categorization with

respect to the reference range will also be presented by frequency tables.

Anti-drug antibodies (ADA)

The analysis of anti-idarucizumab antibodies will be presented in Section 15.8 of the CTR. Only descriptive statistics are planned for this section of the report based on the treated set.

7.8.3 Vital signs

Only descriptive statistics of vital signs (blood pressure, PR, and body temperature) over the time (original value and change from baseline) are planned for this section of the CTR.

7.8.4 ECG

No ECG data are collected in this study.

7.8.5 Others

A frequency table will be provided for local tolerability.

9. ADDITIONAL SECTIONS

Not applicable as no additional information is needed.

10. HISTORY TABLE

This is a revised TSAP including the following modifications to the final TSAP.

Table 10: 1 History table

Version	Date (DD-Mmm-YY)	Author	Sections changed	Brief description of change
Initial	30-Mar-17		None	This is the initial TSAP without any change.
Initial	06-Apr-17		None	No change in the content, but redo the process due to some error in system process.
Final	17-Aug-17		Sections 5, 6 & 7	This is the final TSAP. Some revisions are made upon the initial TSAP in sections 5, 6 and 7.
Revised	14-Sep-17		Section 6.7 & 7.4	Revise the calculation rules for reversal to baseline in section 6.7. Minor change in section 7.4 from “within 2, 4, 6, 12” to “for 2, 4, 6, 12” to be consistent in wording with other studies.
